8.3.2 Mean change from Baseline in platelet count by visit

Mean change from Baseline in platelet count will be summarized descriptively using the RS at each timepoint.

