6.4.3 Rescue therapy

Rescue treatment will be given as per standard of care and at the discretion of the investigator as described below. If such rescue therapy is given, the participant is allowed to continue IMP treatment (as per guidance below), and should continue to complete all remaining scheduled visits in the Treatment Period, as per the Schedule of Activities (Section 1.3). The following rescue therapies may be used:

- Any increase in concomitant ITP therapies above Baseline dose
- Any additional ITP medication/therapies including but not limited to:
 - Platelet transfusion (only in cases of severe bleeding)
 - Commercially available IVIg
 - Any systemically administered corticosteroids (above the background doses, ie, pulse, oral and iv steroids). Any systemic corticosteroids used for the management of infusion reactions or other medical conditions are also considered rescue therapy.
 - Immunosuppressants (except for those listed in Section 6.4.2).

Although the use of rescue therapy is allowable at any time during the study, the use of rescue therapy should be delayed, if possible, for at least 2 days following the administration of study treatment.

If IVIg, high dose corticosteroids, or platelet transfusion are given as rescue therapy, IMP treatment can commence at the same dose as previously when platelet counts are $<50 \times 10^9/L$. Dose can be up-titrated at a later timepoint, if needed, depending on platelet level.

A high dose of corticosteroids is defined as any iv administration of corticosteroids given for any reason or doubling of an oral dose resulting in a dose more than 20mg/day prednisone equivalent dose.

In case of an increase of Baseline oral corticosteroids, not resulting in doubling of the oral dose more than 20mg/day prednisone equivalent dose, an increase in the concomitant ITP therapies above Baseline, or in case of administration of immunosuppressants as rescue therapy, IMP administration can continue as per Schedule of Activities (Section 1.3) at a dose adjusted depending on the platelet level.

The date and time of rescue therapy administration as well as the name and dosage regimen of the rescue therapy must be recorded in the eCRF.

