9.6 Handling of dropouts or missing data

All imputation of missing or partial dates for safety assessments, as well as handling missing efficacy data (where applicable), will be detailed in the SAP.

If individual platelet visit data is missing it will be set to zero; participants who are lost to follow-up will be imputed as nonresponders.

It is not anticipated that there will be missing data, due to the adoption of the responder endpoint definition, where study participants who have not met the threshold for clinically meaningful response will be imputed as nonresponders for the analysis.

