3 DATA ANALYSIS CONSIDERATIONS

3.1 General presentation of summaries and analyses

Statistical analysis and generation of tables, figures, participant data listings, and statistical output will be performed using SAS® Version 9.4 or higher (SAS Institute, Cary, NC, USA).

All tables and listings will use Courier New font size 9.

Descriptive statistics will be displayed to provide an overview of the study results. For continuous variables, descriptive statistics will include number of participants with available measurements (n), mean, standard deviation (SD), the median, minimum, and maximum.

For categorical variables, the number and percentage of participants in each category will be presented. Unless otherwise noted, the denominator for percentages will be based on the number of participants included in the respective analysis set. Participants with missing data can generally be accounted for using the following approaches:

-
- For summaries of demographics and Baseline characteristics: summarize percentages based on all participants in the analysis set and include a “Missing” category (corresponding to participants with missing data for the variable being summarized) as the last row in the list of categories being summarized.
 - For summaries of efficacy and safety variables, unless otherwise specified: summarize percentages based only on those participants with observed data for the variable being summarized. As the denominator may be different from the number of participants in the analysis set being considered, the denominator should be displayed in the table. The general format for displaying this will be “n/Nsub (%)”

Unless otherwise noted, all percentages will be displayed to one decimal place. No percentage will be displayed for zero counts, and no decimal will be presented when the percentage is 100%.

For the purpose of the tabulations the lower and upper confidence limits for the percentages will be truncated at 0 and 100% respectively.

For PK concentrations, summary statistics will include geometric mean, geometric coefficient of variation (CV), 95% confidence intervals (CIs) for geometric mean, arithmetic mean, SD, median, minimum, and maximum. All summaries of PK variables will be based on the observed values. No imputation will be used.

Decimal places for descriptive statistics will always apply the following rules:

- “n” will be an integer
- Mean, SD, and median will use one additional decimal place compared to the original data

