3.9 Changes to protocol-defined analyses

(1) Analysis sets

- (1.2) The FAS was removed from analysis
- (1.3) The PD-PPS was removed from analysis

(2) Added COVID-19 as an intercurrent event to all endpoints

(3) Note: The study was terminated early after 33 participants were randomized to bi-weekly infusions per Protocol Amendment 2; no participants were randomized to weekly infusions in the study per Protocol Amendment 3.

(4) No formal statistical analyses of efficacy endpoints were conducted. Only the primary and secondary efficacy endpoints were summarized descriptively and listed. Protocol-defined analyses for efficacy endpoints are described below.

The primary efficacy analysis of the study was planned to conduct a Stratified Cochran-Mantel-Haenszel test statistic. Sensitivity, supplemental and subgroup analyzes were planned to test the robustness of the assumption. The secondary efficacy analyses were planned to conduct a sequential hierarchical test procedure to protect the overall significance level for the multiplicity of endpoints.

Primary and secondary efficacy endpoints listed below will be listed and summarized descriptively for study participants randomized to bi-weekly dosing according to previous protocol versions.

- Durable Clinically Meaningful Platelet Response of $\geq 50 \times 10^9/L$ for at least 8 out of 12 weeks during the last 12 weeks (Week 13 to 25)
- Cumulative number of weeks with Clinically Meaningful Platelet Response of $\geq 50 \times 10^9/L$ over the 24-week treatment period (Week 1 to Week 25)
- Time to first Clinically Meaningful Platelet Response of $\geq 50 \times 10^9/L$: time from starting treatment to achievement of first response of $\geq 50 \times 10^9/L$
- Clinically Meaningful Platelet Response of $\geq 50 \times 10^9/L$ by Day 8

-
- Response defined as platelet count $\geq 30 \times 10^9/L$ and at least a 2-fold increase of the Baseline count confirmed on at least 2 separate occasions at two adjacent nominal visits at least 7 days apart, and absence of bleeding by visit
 - Time to first rescue therapy
 - Change from Baseline to Week 25 in ITP Patient Assessment Questionnaire (ITP-PAQ) Symptoms Score

Other efficacy endpoints listed below will be listed and summarized descriptively as well.

- Cumulative number of weeks over the planned 24-Week treatment period with platelet counts $\geq 30 \times 10^9/L$ and at least doubling from Baseline
- Mean change from Baseline in platelet count by visit

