4.2 Handling of dropouts or missing data

4.2.1 Handling missing data for the primary and secondary efficacy endpoints

Study participants who have not met the threshold for clinically meaningful response will be imputed as non-responders for the analysis. Missing platelet data at any visit will be considered "worst case" and set to zero ("no response") for that specific visit.

Missing data for ITP Patient Assessment Questionnaire (ITP PAQ) instrument will not be imputed.

Missing efficacy data encountered due to permanent treatment discontinuation due to TEAEs, or the receipt of rescue therapy will be considered as intercurrent events. For the primary efficacy analysis, patients with intercurrent events will be considered as non-responders.

Missing data strategy for PRO related endpoints will follow instructions indicated in each instrument.

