4.2.2 Missing Data due to COVID-19

Unless specified otherwise, study participants who have visits impacted by COVID-19 for any reason will be considered non-responders at the corresponding visit, and missing platelet count data due to COVID-19 will be considered worst case and set to zero ("no response") for that particular visit.

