8.2 Statistical analysis of the secondary efficacy endpoints

8.2.1 Cumulative number of weeks with Clinically Meaningful Platelet Response of $\geq 50 \times 10^9/L$ over the 24-Week treatment period (Week 1 to Week 25)

The secondary efficacy endpoint: Cumulative number of weeks with Clinically Meaningful Platelet Response of $\geq 50 \times 10^9/L$ over the 24-week treatment period will be analyzed on the RS, under the same treatment conditions and population of interest as for the primary endpoint. Note: if platelet count was assessed multiple times in a given week, Clinically Meaningful Platelet Response only needed to be observed at one timepoint during the week. ICE, ICES and population level summary will be handled as described below:

Table 8-2: Intercurrent Events (ICE), Intercurrent Events Strategies (ICES) and Missing data Strategies for the analysis of the Cumulative number of weeks with Clinically Meaningful Platelet Response of $\geq 50 \times 10^9/L$ over the 24-Week treatment period

Intercurrent Events (ICE)	ICE Strategy	Missing data strategy
a) Use of rescue therapy	A while on-treatment strategy: Participants impacted by	Participants impacted by any of the ICE will be considered as having a loss
b) Withdrawal from the study due to treatment emergent AE		

Intercurrent Events (ICE)	ICE Strategy	Missing data strategy
c) Permanent treatment discontinuation	any of the ICE will be considered as having a loss of durable platelet response at the time of the ICE occurring.	of durable platelet response at the time of the ICE occurring. Platelet data up to the start date of this ICE will be utilized in statistical analysis.
d) COVID-19*	A composite strategy: data impacted by COVID-19 will be considered as having a loss of durable platelet response at the time of the ICE occurring.	Section 4.2.2

* COVID-19 Impact category: Temporary discontinuation of study drug, Permanent discontinuation of study drug, Termination of study participation and Relationship to COVID-19: confirmed, suspected, general or other as recorded in the COVID-19 impact eCRF form.

Population-level summary: Owing to early termination of the study, the population-level summary will be provided using descriptive statistics.

8.2.2 Time to first Clinically Meaningful Platelet Response of $\geq 50 \times 10^9/L$: time from starting treatment to achievement of first response of $\geq 50 \times 10^9/L$.

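### The set-to-zero rule for missing platelet counts has no exception for the by-visit mean change in SAP 8.3.2, where a zero becomes a change of minus Baseline

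*SAP*

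**What the plan says.** SAP 8.3.2 is a single sentence: "Mean change from Baseline in platelet count will be summarized descriptively using the RS at each timepoint" (RS is the Randomized Set). It has no intercurrent-event table and no missing-data rule. SAP 8.3.1, directly above it, has both.

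The rules on missing counts stand elsewhere:

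- **SAP 4.2.2**, which applies unless another section specifies differently: "missing platelet count data due to COVID-19 will be considered worst case and set to zero".
- **SAP 3.9(2)**, in the list of changes to protocol-defined analyses: "Added COVID-19 as an intercurrent event to all endpoints".
- **SAP 4.2.1** zeroes missing counts whatever the reason, but its heading is "Handling missing data for the primary and secondary efficacy endpoints". SAP 2.2.1.3 lists mean change as an other efficacy endpoint, so 4.2.1 does not reach it.
- **Protocol 9.6**: "If individual platelet visit data is missing it will be set to zero".
- **SAP 3.1**, for continuous variables: "descriptive statistics will include number of participants with available measurements (n), mean, standard deviation (SD), the median, minimum, and maximum".

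On rescue, protocol 6.4.3 permits IVIg, systemic corticosteroids and, for severe bleeding, platelet transfusion. It asks rescued participants to complete the remaining scheduled visits. For cumulative weeks of response, SAP Table 8-2 says "Platelet data up to the start date of this ICE will be utilized in statistical analysis". SAP 8.3.2 has no equivalent line.

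**The concern.** Zero is a sound conservative code when the endpoint is yes/no or a count of weeks in response: it means that the participant did not respond at that visit. Averaged on the platelet scale it is read as a measured count of zero, and the change from Baseline becomes minus Baseline. The affected mean, SD and minimum then mix measurements with constructed values.

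With no inferential analysis left in the SAP, descriptive tables are all the efficacy evidence this study will report. Mean change is one of only two other efficacy endpoints still summarized. In arms this small, a few constructed values can move a visit mean.

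The rescue question is separate and secondary. Counts raised by rescue are still collected, and 8.3.2 does not say whether they belong in the mean, so a reader cannot tell what quantity the table estimates.

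**Working it through.** The documents give no figure for this endpoint, so there is nothing to reproduce. The check has two parts: which rule applies, and how far a zero can move a mean.

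**1. Which rule applies to a missing count in 8.3.2**

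| Source | Missing because of COVID-19 | Missing for another reason |
|---|---|---|
| SAP 3.1 | left out | left out |
| SAP 4.2.2 with 3.9(2) | zero | not addressed, so 3.1 applies |
| SAP 4.2.1 | not in scope (other endpoint) | not in scope (other endpoint) |
| Protocol 9.6 | zero | zero |

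SAP 4.2.2 yields only to a section that specifies otherwise, and 8.3.2 specifies nothing. SAP 3.1 is a general presentation rule and does not say that it overrides 4.2.2. Three tables are therefore defensible: observed cases, zeros for COVID-19 only, or zeros for every missing visit. If zeros are entered, the n that 3.1 defines (participants with available measurements) no longer matches the denominator of the mean.

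**2. Size of the shift (illustration, ×10⁹/L)**

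Inputs from the documents: 33 randomized (SAP 2.3), 2:1 allocation, and no single Screening or Baseline count above 35 (protocol 5.1, criterion 8). Assumptions: arms of 22 and 11 (33 × 2/3 and 33 × 1/3; the actual split is not stated), Baseline values of 5 to 35, and the numbers of missing counts.

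Let an arm of size N have k missing counts, observed-case mean change m, and mean Baseline b among those missing.

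- Zero-filled mean = [(N − k)m − kb] / N
- Shift from the observed-case mean = −k(m + b) / N

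One missing count with m = 0:

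- Placebo, N = 11: −5/11 = −0.5 to −35/11 = −3.2
- Rozanolixizumab, N = 22: −5/22 = −0.2 to −35/22 = −1.6

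Now assume observed-case means of 30 and 0 (gap 30) and b = 15:

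- Four zeros on rozanolixizumab, one on placebo: (18 × 30 − 4 × 15)/22 = 21.8; −15/11 = −1.4; gap 23.2.
- Two zeros in each arm: (20 × 30 − 2 × 15)/22 = 25.9; −30/11 = −2.7; gap 28.6.
- One zero on rozanolixizumab, four on placebo: (21 × 30 − 15)/22 = 28.0; −60/11 = −5.5; gap 33.4 before rounding.

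The direction depends on which arm has more missing counts.

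**3. Rescue, same assumed setting**

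Assume that a rescued participant shows a change of +85 at the visit, and would otherwise have had the arm's mean change.

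- Three rescued on placebo, two on rozanolixizumab: 3 × 85/11 = 23.2; (2 × 85 + 20 × 30)/22 = 35.0; gap 11.8.
- Five and four rescued: 5 × 85/11 = 38.6; (4 × 85 + 18 × 30)/22 = 40.0; gap 1.4.

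Under these assumptions rescue moves the summary more than the zeros do. The assumption about what would have happened without rescue is generous, because participants are rescued when their counts are low.

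**The case against.** The best case against the zero point is that the rule was never meant for a mean. SAP 4.2.2 speaks of non-responders and glosses zero as no response. Protocol 9.6 leaves missing efficacy data to the SAP and refers to the responder definition. SAP Table 8-3 takes COVID-affected data out of the time at risk, so 3.9(2) does not impose one strategy everywhere. A sensible programmer might simply follow SAP 3.1. That is probably the intention, but it is not what the text says: Table 8-3 states its own handling and 8.3.2 does not. The objection supports the fix.

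On rescue, the objection carries more weight. A reader might infer that the SAP deliberately retains post-rescue counts, and that the difference between arms is therefore not a drug effect. The documents do not support this. Retention follows from silence, and 8.3.2 plans no plot, between-arm contrast or test. Keeping post-rescue counts is also a legitimate treatment-policy summary (assigned arm plus rescue as needed) if declared, although it does not isolate the drug's own effect.

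Nor is exclusion plainly better. Protocol Table 1-1 recommends rescue for repeated counts from 10 to below 30 and recommends it highly below 10, so dropping post-rescue counts leaves a group selected for not needing rescue.

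Finally, the SAP already lists efficacy data by participant and visit and summarizes rescue by arm, so affected counts can be traced.

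**Conclusion.** The zero point holds. As written, SAP 4.2.2 with 3.9(2), and more broadly protocol 9.6, put an artificial change of minus Baseline into a continuous mean, and SAP 3.1 conflicts with this without settling it. The rescue point holds only as an omission: 8.3.2 names no strategy.

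A reader might take the illustrative gaps as estimates of actual distortion. They are not: the documents give neither COVID-missing nor rescue counts, and the 22/11 split, Baselines and changes are assumed. For zeros alone, one missing count moves an arm mean by 0.2 to 3.2 when the observed mean change is 0, and by more when it is positive. The consequence is limited, because this is an other efficacy endpoint, summarized descriptively, in a terminated study of 33 participants with no decision attached. The correction is still worthwhile because it is nearly free and removes a real ambiguity from the output.

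**What to change.** 1. **SAP 4.2.2:** limit the set-to-zero rule to responder and weeks-of-response endpoints. SAP 14.1 attributes the COVID-19 zero rule to an FDA request; it stays in force for those endpoints. The sponsor should confirm that the request was not meant for the continuous mean.
2. **SAP 8.3.2:** state that missing counts are not imputed, whatever the reason, and that each visit is summarized on observed cases. Showing n per visit is already required by SAP 3.1.
3. **SAP 3.9:** record the departure from protocol 9.6 for this endpoint.
4. **SAP 8.3.2, rescue:** declare the main summary as treatment-policy (all observed counts, including those after rescue). Add a companion summary that excludes counts from the start of rescue, with a note that the remaining participants are a selected group.

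The cost is a few sentences, one filter and one extra table. An observed-case mean has a smaller n at later visits and is itself open to selection if counts are missing for reasons related to response; the displayed n makes the extent of missing data visible.

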8.4 Statistical analysis of exploratory endpoints

All exploratory variables will be listed only by treatment group and visit. No inferential assessments / testing will be performed.

8.4.1 ITP Bleeding Score

8.4.1.1 ITP-specific Bleeding Assessment Tool (ITP-BAT) bleeding events and severity by visit

ITP-BAT bleeding events by visit, will be listed using the RS.

Table 8-7: ITP-specific Bleeding Assessment Tool (ITP-BAT) Domains and categories

Skin	Mucosal	Organ
- Petechiae	- Epistaxis	- Gastrointestinal Bleeding Not Explained by Visible Mucosal Bleeding or Lesion
- Ecchymoses	- Oral cavity [a]	- Lung Bleeding
- Subcutaneous Hematomas	- Subconjunctival Hemorrhage	- Hematuria
- Bleeding from Minor Wounds		- Menorrhagia
		- Intramuscular Hematomas
		- Hemarthrosis
		- Ocular Bleeding
		- Intracranial Bleeding
		- Other Internal Bleedings

[a] Includes gum bleeding, hemorrhagic bullae or blisters, bleeding after bites to lip & tongue or after deciduous teeth loss

Notes:

- Presence of bleeding will be indicated by a Mucosae or Organs Grade ≥ 1 , or Skin Grade ≥ 2 .
- Bleeding reported by the participant without medical documentation will be graded 1.
- Within each domain, the same grade is assigned to bleeding manifestations of similar clinical impact.
- The “worst” bleeding manifestation since the last visit will be graded, and the highest grade within each domain will be recorded.

Please see Section 13.6 ITP bleeding score for more details.

8.4.1.2 ITP bleeding at Screening

Data collected in the Bleeding Assessment Tool – Screening eCRF will be listed using the RS.

8.4.1.3 Presence/Absence of ITP bleeding

The number and percentage of participants with absence/presence of bleeding (see definitions below) will be summarized, and individual participants will be listed at each visit.

- Presence of bleeding is indicated by a Grade of 1 or above, for at least one domain of the SMOG (except for Skin, where it is Grade 2 or above).
- Absence of bleeding is indicated by Grade 0 for all domains of the SMOG, or a Skin Grade of 0 or 1

8.4.2 Effect of Rozanolixizumab on Health-Related Quality of Life (HRQoL)

8.4.2.1 European Quality of Life-5 Dimensions, 5 Levels (EQ-5D-5L) item responses

As described in section 8.1.3.4 in the protocol, the EQ-5D-5L health questionnaire consists of 2 pages: the EQ-5D descriptive system and the EQ visual analogue scale (EQ VAS).

The descriptive system comprises five dimensions: mobility, self-care, usual activities, pain/discomfort and anxiety/depression. Each dimension has 5 levels: no problems, slight problems, moderate problems, severe problems and extreme problems. The patient is asked to indicate his/her health state by ticking the box next to the most appropriate statement in each of the five dimensions. This decision results in a 1-digit number that expresses the level selected for that dimension. The digits for the five dimensions can be combined into a 5-digit number that describes the patient's health state.

The EQ VAS records the patient's self-rated health on a vertical visual analogue scale, where the endpoints are labelled 'The best health you can imagine' and 'The worst health you can imagine'. The VAS can be used as a quantitative measure of health outcome that reflect the patient's own judgement.

The EQ-5D-5L essentially consists of 2 pages: the EQ-5D descriptive system and the EQ visual analogue scale (EQ VAS).

Observed values in the European Quality of Life 5 Dimension 5 Levels (EQ 5D 5L) item responses and VAS scores will be listed only.

